 - A description of each adverse event by type, severity, time of detection (days post-application and/or post-removal) captured as date AE is diagnosed, clinical management, and resolution. The likelihood of relatedness to having undergone VMMC and relatedness specifically to the ShangRing device will be determined. AEs will be defined using the definitions in the second edition of the VMMC Adverse Event Action Guide.²⁴ These are specific to each AE type, but in general:
 - Mild: classification indicates minimal or no intervention is required beyond reassurance and observation;
 - Moderate: classification relates to those AEs that are neither mild nor severe, require intervention, and are usually managed on-site;
 - Severe: classification requires extensive intervention with referral or specialist input.
 - Note: a Serious Adverse Event (SAE) is a standard definition used across many types of interventions. In the context of VMMC, all AEs that meet criteria for severe should also be classified as SAEs. In addition, SAEs also include any event that:
 - Results in death

- Is life threatening
- Requires intervention to prevent permanent disability or incapacitation (including deformity), or results in permanent disability or incapacitation (including deformity)
- Requires hospitalization or referral to a specialist for higher level care or intervention.
- (Note: device displacement is included as an AE both in the moderate and severe classifications – see Appendix XV).

Secondary Endpoints

- Determine the training needed for proficiency, including number of procedures required under supervision to become certified as fully proficient. This will involve analyzing AE rates stratified by during training and post-training in addition to overall.
 - Determining whether various cadres are trainable as safe providers. This would involve analyzing AE rates stratified by provider cadre.
- Document client acceptability and satisfaction, to be measured by the following:
 - Time for client to return to normal activity, including work and routine tasks.
 - Clients' opinions of convenience (having device applied, 'wearing' the device for a week, and returning for device removal), acceptability, cosmetic result, and whether they would recommend VMMC, and specifically the ShangRing VMMC option to others.

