Procedure for Handling Clients Lost-to-Follow-Up

Clients who are lost to follow-up after device placement, and therefore do not return to have the device removed, will not be recorded as experiencing an AE, and also will not be included in calculations when measuring AEs.

In the event that a client refuses to return for follow-up, ShangRing has been shown to detach on its own. Studies show that for those clients who do not come in to have the device removed, and wear it for more than

seven days, the ShangRing will eventually spontaneously detach on its own, and healing will progress normally. In one study, complete detachment of the device occurred in 66.7% of men who wore the device for more than seven days, and 14% of men requested removal of a partially detached device 8-14 days after placement. No severe or serious AEs were reported among this group.²⁹

A study of delayed removal of ShangRing in Kenya found that in 81.8% of men the ShangRing had completely detached on its own between 10-16 days after circumcision.³⁰ By 21 days following the circumcision the ring had at least partially detached in 100% of men, and was completely detached in 93.7%. While the ShangRing has been found to be safe if left on, this is not the recommended standard of care for the purposes of this evaluation, and clients will be followed up with for device removal as described in this protocol.

Provider Participant Inclusion Criteria

Providers meeting the following criteria will be included in the evaluation:

- Adult aged 18 or older
- Employed as a medical doctor, Assistant Medical Officer, Clinical Officer, professional nurse, or enrolled nurse at the participating sites in Shinyanga, Tanzania
- Experienced in providing conventional surgical circumcision
- Trained and certified in ShangRing circumcision techniques for the current evaluation by a trainer who is trained in ShangRing application, and has performed a minimum of 10 placements and 5 removals. The evaluation team will bring in ShangRing master trainers from countries with prior ShangRing experience (i.e. Kenya, Zambia) to train providers based in Shinyanga who will then train mid-level providers to conduct ShangRing circumcision, or send physicians from Tanzania to these countries for training.
 - Trained and competent in identifying and managing complications related to ShangRing circumcision.
 - Trained and competent in screening clients to determine their eligibility for ShangRing circumcision.

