- Providers are able to demonstrate competence in ShangRing procedure upon completion of the course as described below.
- Providers are trained and competent in screening clients to determine their eligibility for ShangRing circumcision.
- Agrees to complete evaluation surveys and focus group discussions at midpoint of the evaluation, following at least 4 weeks of client enrollment.
- Ability to communicate in English and/or Swahili.
- Capable and willing to provide written informed consent to participate

Provider Participant Exclusion Criteria

Providers with the following criteria will be excluded from the evaluation:

- Failure of ShangRing training, as determined by the instructors at the end of the training period
- Failure to comply with universal precautions for infection prevention and control
- Failure to provide written informed consent

Minimum Site Requirements for ShangRing Pilot Service Delivery

Sites in Shinyanga, Tanzania were selected upon their ability to provide safe male circumcision services and on the basis of meeting minimum readiness requirements necessary to provide ShangRing service delivery. These requirements are as follows:

- Prior to the beginning of the evaluation, at least some providers are trained and competent in conventional surgical male circumcision. This is because there is a risk that ShangRing circumcision will

need to be converted to surgical intervention in the event of certain AEs (e.g., uncontrolled, bleeding), device malfunction or displacement. This criterion may change with further experience demonstrating whether this risk materializes.

- Site is equipped for emergency clinical management of immediate and post-procedure complications.
- Site has an agreed-upon referral plan to a district, sub-district or other facility where providers with skills to manage rare complications are available.
- All supplies for ShangRing placement and removal are reliably available.
- Site is capable of complying with relevant national policies on tetanus immunization for VMMC by both device-based and conventional surgical methods, as applicable.

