ShangRing devices and medical instruments for placement and removal will be supplied to each partner at the beginning of the evaluation pilot. Partners will be responsible for further distribution to their pilot sites. Depending on actual consumption, disbursed supplies may be recalled for redistribution to match supply with demand at each site. A total of 750 devices will be purchased in various sizes to allow for the 575 procedures to be performed, as well as those performed during the training phase.

Evaluation Phases

Training Phase

During the training phase, clinicians at participating sites will be trained in the use of the ShangRing device by “master trainer” clinicians who have previous experience with the ShangRing device. This training phase will be used to evaluate the training requirements for implementation by mid-level providers, and to preliminarily assess acceptability to providers and clients and monitor logistical needs. Each clinician will perform no fewer than 10 ShangRing device placements, and 5 ShangRing removals before the start of the implementation pilot. Between 8 and 12 providers will be trained, meaning the number of clients receiving ShangRing during this time will be approximately 80-120. The clinicians trained in the master trainers will then train midlevel providers at the participating sites (anticipated to be another 2-4 providers at each site). Implementation pilot data will be collected from the clients receiving circumcisions with the ShangRing device during the training phase.

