When each physician's ShangRing skills are found acceptable by passing a training course and theoretical, practical and clinical tests, s/he will be certified by the training provider as competent. The newly certified Tanzanian physicians will then assist in training mid-level providers (registered and enrolled nurses) in Tanzania.

Mid-Level Provider Training

An integrated team, led by the TOTs and assisted by the recently ShangRing trained Tanzanian physicians, will conduct the training for mid-level providers (defined as registered and enrolled nurses) in Tanzania. In this phase of evaluation activities, each trainee mid-level provider will also successfully perform 10 placements and 5 removals before being deemed competent. All ShangRing procedures in this group will be closely supervised and

tutored by the integrated training team described above. When each trainee provider's ShangRing skills are found acceptable by passing a training course and theoretical, practical and clinical tests, s/he will be certified by the integrated training team as competent and permitted to participate in the evaluation as a ShangRing evaluation provider. Additionally, by having the recently trained Tanzanian physicians assist in the training of mid-level providers, the Tanzanian physicians will be better able to conduct future trainings in the event of ShangRing scale-up. All outcomes data during the training phase will be collected per the protocol as part of their training, but will not be included in the analysis.

Additional Staff Training

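### Failing ShangRing training excludes a provider from an evaluation whose first phase is that training; read literally, provider-level training results come only from those who passed

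*Protocol*

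**What the plan says.** Four statements tie provider membership to passing the training.

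- Provider Participant Exclusion Criteria: "Providers with the following criteria will be excluded from the evaluation", and the first criterion is "Failure of ShangRing training, as determined by the instructors at the end of the training period".
- Provider Participant Inclusion Criteria: a provider must be "Trained and certified in ShangRing circumcision techniques for the current evaluation".
- The same list: "Providers are able to demonstrate competence in ShangRing procedure upon completion of the course as described below".
- Mid-Level Provider Training: a trainee who passes is "certified by the integrated training team as competent and permitted to participate in the evaluation as a ShangRing evaluation provider".

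Training is itself part of what is evaluated. The Overall Design makes it one of two phases, and the Training Phase section states: "This training phase will be used to evaluate the training requirements for implementation by mid-level providers". The Secondary Endpoints include the "number of procedures required under supervision to become certified as fully proficient" and "Determining whether various cadres are trainable as safe providers". The latter is to be assessed through AE rates by provider cadre. For Phase 1, Table 2 lists provider training needs, acceptability and proficiency among the primary endpoints, and training satisfaction and needs among the secondary ones.

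On training-phase data the sections differ. Physician Training puts all client data from the training phase into the final analysis. Mid-Level Provider Training says that training-phase outcomes are collected but not analysed.

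**The concern.** A study of how much training proficiency takes has to include the people who did not reach proficiency. Here, eligibility is settled by the outcome being measured. If failures are removed, the number of procedures to certification is summarised over successes only and is biased downward. Opinions on the training come only from those for whom it worked; if those who failed would rate it lower, as seems likely, satisfaction is biased upward.

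Mid-level providers are where this matters most. The first evaluation objective concerns safety when trained mid-level providers perform the circumcision, and the Justification for Evaluation names provider training among the national policy decisions to be informed. If a cadre finds the device hard to learn, that is where failures would occur and where removing them would mislead most.

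The protocol asks for the number and reasons of client exclusions and withdrawals to be reported. It has no matching requirement for providers who start training and fail.

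**Working it through.** **1. Who remains, and when.** The exclusion is judged at the end of training. The provider surveys and group discussions named in the inclusion criteria take place at the evaluation midpoint, after at least four weeks of client enrolment. The provider survey (Appendix XXVI), which contains the training questions, is addressed to those who took part as a provider. A trainee who failed has by then left the evaluation as the criteria define it.

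**2. Endpoint by endpoint, reading the criteria literally.**

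| Endpoint | Effect of the exclusion |
|---|---|
| Supervised procedures to certification | Failures absent; summary over successes only |
| Training questions in the provider survey | Failures absent |
| Phase 1 provider interview (Appendix XXIV) | Unclear: given on completion of training, with no certification condition |
| AE rates, physician training | Not clearly affected: Physician Training keeps all client data |
| AE rates, mid-level training | Training-phase outcomes of all mid-level trainees are left out, so only procedures by certified operators remain |

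**3. Text pointing the other way.** Besides Physician Training, the Data Collection section gathers test results, AE and incident rates and procedure times on trainees. The Analysis Overview reports AE rates for training, post-training and overall. Reimbursements refers to interviews with all providers trained. None of these sections amends the eligibility criteria. They show that the protocol does not settle whether a failed trainee is a participant.

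**4. The plan's own figures.** The Training Phase section gives 8 to 12 trainees with at least 10 placements each: 8 × 10 = 80 and 12 × 10 = 120, matching the stated 80 to 120 clients. It anticipates another 2 to 4 mid-level providers per site. With two sites that is 2 × 2 = 4 to 2 × 4 = 8. If these are additional to the 8 to 12, their training covers at least 4 × 10 = 40 to 8 × 10 = 80 placements, which Mid-Level Provider Training leaves out of the analysis.

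**5. Illustration of the provider-level loss.** No failure rate is given, so the number of failures is assumed. Certified proportion = (started − failed) / started, with exact (Clopper-Pearson) 95% limits:

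| Started | Failed | Certified | 95% CI |
|---|---|---|---|
| 8 | 1 | 7/8 = 87.5% | 47.3 to 99.7 |
| 8 | 2 | 6/8 = 75.0% | 34.9 to 96.8 |
| 12 | 1 | 11/12 = 91.7% | 61.5 to 99.8 |
| 12 | 2 | 10/12 = 83.3% | 51.6 to 97.9 |

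Among passers alone the proportion is 100% whatever happened. In a cadre of 4, one failure is 3/4 = 75%. The intervals are wide, so the value of reporting these counts is descriptive.

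**The case against.** The strongest reply is that the exclusion is only an operator gate. It takes effect after training, when Phase 1 data already exist, and nothing says that data from a failed trainee are discarded. Being permitted to act as an evaluation provider describes a role. On that reading the sections on trainee data and interviews are consistent with the criteria. This may well be the intention, but the criteria say excluded from the evaluation, of which training is a part. The reference to interviews with all trained providers is incidental to a sentence about refreshments.

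A reader might infer that every training endpoint is computed only on those who passed, so that trainability is 100% in each cadre by construction. The documents do not support that. No pass rate is a stated endpoint; cadre trainability is judged by client-level AE rates, which passing does not fix at any value. Physician training data are kept without an exception for failures. Nor does the protocol say that failures miss the Phase 1 interview.

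It can also be said that denominators and the handling of failures belong in a statistical analysis plan, which is not at hand. That stands for the detail of the summaries. It does not stand for eligibility: the protocol decides who is a participant, and an analysis plan cannot restore people whom the criteria remove.

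**Conclusion.** The point holds at provider level. As worded, the criteria select on the outcome for procedures to certification and for the training questions in the provider survey, in the favourable direction. For mid-level providers, the statement that training-phase outcomes are not analysed leaves AE-based trainability resting on certified operators, contrary to the Secondary Endpoints and the Analysis Overview. AE rates from physician training are not clearly affected.

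The size cannot be computed without a failure rate; if nobody fails, the provider-level selection is nil. One assumed failure among 8 to 12 trainees means 87.5% to 91.7% certified, and two mean 75.0% to 83.3%. The conclusion rests on the literal wording. If the exclusion was meant only to govern who operates in Phase 2, the defect is one of wording, but it still needs correcting because two teams could follow this protocol and report different training results.

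**What to change.** - Split the provider criteria by phase. Every consenting provider who starts ShangRing training is a Phase 1 participant. The certification, competence and failure criteria apply only to performing procedures in Phase 2, so the existing bar on uncertified operators in that phase is unchanged.
- Report the number started and the number certified, by cadre.
- In procedures to certification, count a failure as not certified after the number of procedures performed.
- Offer failures the Phase 1 interview and the training section of the provider survey.
- Reconcile Physician Training and Mid-Level Provider Training with each other, and both with the Secondary Endpoints and the Analysis Overview, so that training-phase outcomes of all trainees, mid-level providers included, enter the training and cadre analyses.

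The cost is rewording two criteria lists and the data statements, plus a short reporting table. Trainee test results, AE rates and procedure times are already to be collected. The downside is a possibly less favourable training result.
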